#### **Hypothesis Testing**

With respect to Acceptable lens fit the null and alternative hypothesis for superiority is as follows:

$$H_o: p_T \le 0.90$$
  
 $H_A: p_T > 0.90$ 

Where,  $p_T$  represents the proportion of subject eyes that achieve acceptable fit for the Test lens. Success for acceptable fit will be declared if the lower bound of the 2-sided 95% credible interval of the proportion is greater than 0.90; i.e.  $P(p_T > 0.90) \ge .975$ . If the full planned model fails to converge, reduced versions may be considered.

#### **Slit Lamp Findings**

Grade 3 or higher slit lamp findings will be analyzed using a Bayesian Logistic regression random-effects model to compare the Test and Control lenses. The regression model will include baseline slit lamp findings and lens type. Site and subject will be included in the model as random effects.

Let  $y_{ijkl}=1$  if a Grade 3 or higher SLF is observed and  $y_{ijkl}=0$  otherwise for the  $l^{th}$  subject, from the  $k^{th}$  site, assigned to the  $i^{th}$  study lens for the  $j^{th}$  eye.

yijkl ~ Binary (pijkl)

$$p_{ijkl} = \frac{\exp(\beta_0 + \beta_1 Lens_i + \beta_2 Baseline SLF_1 + \gamma_k + \delta_l)}{1 + \exp(\beta_0 + \beta_1 Lens_i + \beta_2 Baseline SLF_1 + \gamma_k + \delta_l)}$$

We assume the random effect for subject are i.i.d as  $\delta_{l} \sim N(0, \sigma_{subject}^{2})$  for the random for clinical site are i.i.d as  $\gamma_{k} \sim N(0, \sigma_{site}^{2})$  for i=1,2 (lens), j=1, 2 (eye), k=1, 2, 3, 4, 5, 6 (site) and l=1,...n (subject/site).

In this model, we define  $Lens_i=0$  for the Control lens and  $Lens_i=1$  for the Test lens. For the  $\beta$  coefficients, independent non-informative priors N(0,1000) will be used. For the variance of random effects of  $\sigma_{subject}^2$  and  $\sigma_{site}^2$ , independent non-informative conjugate priors inverse-gamma (0.001, 0.001) will be used. The Metropolis-Hastings algorithm as implemented in the SAS/STAT 14.2 PROC MCMC procedure will be used to estimate posterior distributions of the unknown parameters. Inferences will be made based on the posterior credible interval for the relevant parameters.

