3.2. Inclusion Criteria

Potential subjects must satisfy all of the following criteria to be enrolled in the study:

Inclusion Criteria after Screening

- 1. The subject must read, understand, and sign the STATEMENT OF INFORMED CONSENT and receive a fully executed copy of the form.
- 2. Appear able and willing to adhere to the instructions set forth in this clinical protocol.
- 3. Between 18 and 49 (inclusive) years of age at the time of informed consent.
- 4. Eligible presbyopes will be those that wear full distance contact lenses in both eyes, then wear reading glasses over them when needed for near vision.
- 5. The subject is a current spherical soft contact lens wearer in both eyes with a minimum of 6 hours/day and 5 days/week wear time over the last 30 days by self-report.
- 6. Subjects must be able and willing to wear the study lenses at least 6 hours a day, a minimum of 5 days per week
- 7. Subjects must own a wearable pair of distance spectacles.

Inclusion Criteria after Baseline

- 8. The subject's vertex-corrected spherical equivalent distance refraction must be in the range of -1.00 to -6.00 D (inclusive) in each eye.
- 9. The subject's refractive cylinder must be 0.00 to -1.00 D (inclusive) in each eye.
- 10. The subject must have a spherocylindrical best corrected distance Snellen visual acuity of $20/25^{+3}$ or better in each eye.

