#### **Hypothesis Testing**

The null and alternative hypothesis for Non-inferiority is as follows:

$$\begin{array}{l} H_0 \ p_T - \ p_C \ge 0.05 \\ H_A \ p_T - \ p_C < \ 0.05 \end{array}$$

Where  $p_T$  and  $p_C$  are the proportions of eyes with Grade or higher SLFs for the Test group and Control group, respectively. Non-inferiority will be established if the upper limit of the 2-sided 95% credible interval is below 5%, i.e.  $\Pr(p_T - p_C < 0.05 | y) = 0.975$ .

If the full planned model fails to converge, reduced versions may be considered. In the event that the number of Grade 3 or higher SLFs is too small Grade 2 or higher SLFs will be analyzed and tested as described above.

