# Where,

ads\_VS =analysis data set for Vision Satisfaction in Bright Lighting trtan= numerical representation of treatment, where Test=1 and Control=0

```
CR-6305, Statistical Analysis Plan Version 1.0
```

age= Age of subject at time of consent sexn= Numerical representation of sex, where Female=1 and Male=0; siteid= Site Number

Lens Fit

```
PROC MCMC DATA=ads_LF DIC MCHISTORY=brief

NBI=50000 NMC=200000 THIN = 50 STATS=ALL plots(smooth) MONITOR=(_parms_)

OUTPOST =post STATS(ALPHA=(0.05) PERCENTAGE=(2.5 25 50 75 97.5) ) SEED=53457 ;

ODS OUTPUT PostSummaries = PostSummaries ;

ODS OUTPUT PostIntervals = PostIntervals ;

BY trta;

PARM p 0.5 ;

PARM ro .6 ;

PRIOR ro ~uniform(0,1);

PRIOR p ~ beta(0.5, 0.5);

;

llike = log( (1-ro)*PDF('BINOMIAL', y, p, 2) + z*ro*(PDF('BINOMIAL',y,p,2)**0.5));

MODEL y ~ GENERAL(llike);

RUN;

Slit lamp Findings (Grade 3 or higher)
```

```
PROC MCMC DATA=ads SLF DIC MCHISTORY=brief

NBI=100000 NMC=500000 THIN =100 STATS=ALL plots(smooth) MONITOR=(_parms_

P C P T)

OUTPOST =post STATS(ALPHA=(0.05) PERCENTAGE=(2.5 25 50 75 97.5)) SEED=53457 ;

ODS OUTPUT PostSummaries = PostSummaries ;

ODS OUTPUT PostIntervals = PostIntervals ;

PARMS (beta0 beta1 beta2 beta3) 0 sigma_site 1 sigma_subject 1;

PRIOR beta: ~NORMAL(0, var=1000);

PRIOR sigma_site~ IGAMMA(shape=0.01, scale=0.01);

PRIOR sigma_subject ~UNIFORM(0,100);
```

```
RANDOM gamma site ~NORMAL(0, var=sigma site) SUBJECT=siteid;
RANDOM gamma_subject ~NORMAL(0, sd=sigma_subject) SUBJECT=site_subjid;
```

 $mu = beta0 + beta1*trtan + beta2*age + beta3*sexn + gamma_site + gamma_subject;$ 

p = logistic(mu);

MODEL  $y \sim BINARY(P);$ 

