### BEGINNODATA;

P C = logistic(beta0 + 0.5\*beta3); P\_T = logistic(beta0 + beta1 + 0.5\*beta3);

Diff = P T - P C; ENDNODATA; run;

Where, ads SLF =analysis data set for Slit Lamp Findings trtan= numerical representation of treatment, where Test=1 and Control=0 age= Age of subject at time of consent sexn= Numerical representation of sex, where Female=1 and Male=0; siteid= Site Number site\_subjid=Unique Subject ID

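### The slit lamp code drops the baseline covariate specified in SAP 10.1, adds age and sex, and evaluates the primary safety difference at age 0

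*SAP*

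**What the plan says.** **Model in the text.** SAP 10.1, Slit Lamp Findings, puts in the regression model "baseline slit lamp findings and lens type". The equation there has an intercept, lens, a baseline SLF term and random effects for site and subject. Protocol 14.5 has the same terms. Both variance components get inverse-gamma(0.001, 0.001) priors. The test compares the upper limit of the 95% credible interval for the difference in proportions (Test minus Control) with 0.05.

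**Model in the code.** SAP 14.1: "mu = beta0 + beta1*trtan + beta2*age + beta3*sexn + gamma_site + gamma_subject". The variable list beneath it includes "age= Age of subject at time of consent" and "sexn= Numerical representation of sex, where Female=1 and Male=0", and it defines no baseline variable. The Control probability begins "P C = logistic(beta0 + 0.5", multiplied by the sex coefficient. The Test probability adds the lens coefficient. Neither contains the age coefficient. The code also uses Uniform(0,100) for the subject SD and inverse-gamma(0.01, 0.01) for the site variance. Diff is computed but is not in the MONITOR list, which names the parameters, P_C and P_T.

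**Surrounding rules.** If the number of "Grade 3 or higher SLFs is too small Grade 2 or higher SLFs will be analyzed" by the same method. If the full model fails to converge, reduced versions may be considered. SAP 1 ranks the SAP above the protocol but does not rank SAP text against SAP code. Protocol 3.2 enrols "Between 18 and 49 (inclusive) years of age at the time of informed consent".

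**The concern.** Two analysts could each follow the SAP and fit different models to a primary safety endpoint. All five primary hypotheses must be met (SAP 4.1), so this one test can decide the study.

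The covariate mismatch also has a numerical consequence. In the visual acuity and comfort code the age term is likewise left out of the two predicted means, but those models are linear, so it cancels in the difference. The slit lamp model is logistic, so it does not cancel. The risk difference for a fixed lens odds ratio depends on the age at which it is evaluated, and the code evaluates it at age 0, where there are no data.

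**Working it through.** The plan prints no figure for this contrast. Its one slit lamp figure, 80% power, comes from a lens-only model and does not bear on the point.

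**1. Text against code**

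| Element | SAP 10.1 | SAP 14.1 code |
|---|---|---|
| Lens | yes | yes |
| Baseline SLF | yes | no |
| Age, sex | no | yes |
| Subject prior | inverse-gamma(0.001, 0.001) on variance | Uniform(0,100) on SD |
| Site prior | inverse-gamma(0.001, 0.001) | inverse-gamma(0.01, 0.01) |

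The visual acuity, comfort and bright-lighting sections each allow further subject characteristics where appropriate. The slit lamp section has no such allowance. The convergence clause permits a smaller model, not two added covariates.

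**2. What the code evaluates**

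- Fitted: logit p = b0 + b1·lens + b2·age + b3·sex + site + subject.
- Reported: P_C = logistic(b0 + 0.5·b3) and P_T = logistic(b0 + b1 + 0.5·b3).
- The reported values are therefore at age = 0, sex = 0.5 and random effects = 0.
- Sex is coded 0/1 and 0.5 lies within its range, so its coding does no comparable damage.

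**3. Size of the age-0 effect**

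Assumptions, not in the documents: true rates of 5% (Control) and 10% (Test) at age 33.5, the midpoint of 18 to 49, and an age slope s between -0.05 and +0.05 logit per year. Then p(0) = logistic(logit p(33.5) - 33.5·s), with logit 0.05 = -2.944 and logit 0.10 = -2.197.

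For s = +0.03 the shift is -1.005, so P_C = logistic(-3.949) = 1.89%, P_T = logistic(-3.202) = 3.91%, and the difference is 2.0 points.

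| s (logit/year) | P_C at age 0 | P_T at age 0 | Difference (points) |
|---|---|---|---|
| -0.05 | 21.9% | 37.2% | 15.3 |
| -0.03 | 12.6% | 23.3% | 10.7 |
| 0 | 5.0% | 10.0% | 5.0 |
| +0.03 | 1.9% | 3.9% | 2.0 |
| +0.05 | 1.0% | 2.0% | 1.1 |

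The lens odds ratio is 2.11 in every row.

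**4. Effect on the decision**

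Simulation: 112 subjects per arm, two eyes with correlation 0.70 (the SAP 7.4 value), ages uniform on 18 to 49, 1,500 trials per scenario, and a normal approximation to the posterior without random effects. The true rates at age 33.5 are 10% and 5%, exactly on the margin, so non-inferiority should be declared about 2.5% of the time.

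| s | Declared, age 0 (as coded) | Declared, mean age |
|---|---|---|
| -0.05 | 0.4% | 3.8% |
| -0.03 | 0.5% | 2.4% |
| 0 | 4.8% | 3.1% |
| +0.03 | 19.3% | 2.4% |
| +0.05 | 38.5% | 2.9% |

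Extrapolation costs precision even without an age effect. With equal 5% rates and s = 0, the median 95% interval width is 0.217 at age 0 against 0.111 at mean age, and non-inferiority is declared in about 33% of trials against 45%.

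**The case against.** **Age might be centred in the analysis dataset.** Then age 0 would mean average age and the problem would disappear. The SAP does not say so: its variable list defines age as age at consent.

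**The text may govern.** The Grade 2+ fallback is to be tested as described in 10.1, which points to the text. So a reader might infer that the coded model is the one that will run, but the documents do not establish that. What they establish is a conflict with no stated precedence.

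**Baseline adjustment may matter little.** This largely stands. Grade 2 or worse is excluded at baseline (protocol 3.3), so only Grades 0 and 1 remain. A reader might infer that chance imbalance in baseline Grade 1 biases the comparison against the 5-point margin. It does not: under randomisation that imbalance is sampling error which the unadjusted interval already covers. Adjustment buys precision, chiefly in the Grade 2+ fallback. That fallback is plausible, since SAP 7.4 reports no Grade 3+ findings in 860 Test and 270 Control eyes. The documents give no baseline Grade 0/1 split, so the gain can only be illustrated. Take the historical Test Grade 2 rate of 13.5% in both arms and carry over the 0.70 eye correlation. The SE of the difference is sqrt(2 × 0.135 × 0.865 × 1.7/224) = 4.2 points. Assume half of subjects start at Grade 1. The variance removed by adjustment is (2 × 0.25/112) × gap², where gap is the Grade 2+ risk difference between baseline grades. Gaps of 0, 15 and 27 points (the last is the largest compatible with 13.5% overall) give SEs of 4.2, 4.1 and 3.8.

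**Too few events for age and sex.** A reader might also infer that these two coefficients cannot be estimated. With sparse Grade 3+ events the same would be true of a baseline coefficient. In the fallback, 13.5% of 448 eyes is about 60 events, enough for two more terms. This is no separate argument against them.

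**Conclusion.** The conflict between SAP 10.1 and the SAP 14.1 code is definite and rests on no assumption: one specified covariate is missing, two unspecified ones are present, and both variance priors differ. As coded, with age as defined, the primary safety difference refers to age 0.

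Its size depends on an age slope that the documents do not give. For slopes of ±0.03 logit per year, a true 5-point difference at age 33.5 is evaluated as 2.0 or 10.7 points. The error can go either way, so it should not be read as favouring the Test lens. With no age slope the target difference is right but its interval is about twice as wide. The simulated rates also rest on a uniform age distribution and an approximation without random effects, so they indicate direction and order of size rather than exact operating characteristics.

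The missing baseline term is a minor loss of precision. The point should be fixed before database lock.

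**What to change.** 1. Make the code match SAP 10.1: remove age and sex and add the baseline SLF term.
2. Define that term. SAP 11.6 lists several graded findings, and 10.1 does not say how they combine or whether the value belongs to the eye or the subject. One option is an indicator per eye of any Grade 1 finding against none, since higher grades are excluded at baseline.
3. Compute P_T and P_C in each posterior draw by averaging predictions over the observed covariate values, then take the difference. Say also how the random effects are handled: 10.1 describes proportions of eyes, and predictions at zero random effects are not that quantity.
4. If age is to stay, add it to 10.1 with a reason and evaluate at observed ages.
5. Use one set of variance priors in both places and add Diff to the MONITOR list.
6. State whether SAP text or code governs if they differ. Check the bright-lighting code too, as it also omits the age term inside a logistic prediction.

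The cost is a short SAP amendment, one derived variable and a few lines of code. Baseline biomicroscopy is already collected at Visit 1, so no new data are needed.

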#### **Hypothesis Testing**

The null and alternative hypothesis for Non-inferiority is as follows:

$$\begin{array}{l} H_0 \ p_T - \ p_C \ge 0.05 \\ H_A \ p_T - \ p_C < \ 0.05 \end{array}$$

Where  $p_T$  and  $p_C$  are the proportions of eyes with Grade or higher SLFs for the Test group and Control group, respectively. Non-inferiority will be established if the upper limit of the 2-sided 95% credible interval is below 5%, i.e.  $\Pr(p_T - p_C < 0.05 | y) = 0.975$ .

If the full planned model fails to converge, reduced versions may be considered. In the event that the number of Grade 3 or higher SLFs is too small Grade 2 or higher SLFs will be analyzed and tested as described above.

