3.3. Exclusion Criteria

Potential subjects who meet any of the following criteria will be excluded from participating in the study:

Exclusion Criteria after Screening:

- 1. Currently pregnant or lactating (subjects who become pregnant during the study will be discontinued).
- 2. Any active or ongoing systemic disease (e.g., Sjögren's Syndrome), infectious disease (e.g., hepatitis, tuberculosis), contagious immunosuppressive diseases (e.g., HIV), autoimmune disease (e.g. rheumatoid arthritis).
- 3. Subjects taking suspect oral medications for less than one year. (See Section 3.3.1 for suspect medications and more details).
- 4. Any prescribed or over the counter (OTC) ocular medication.
- 5. Any known hypersensitivity or allergic reaction to Optifree® PureMoist® multi-purpose care solution or Eye-Cept[®] rewetting drop solution.
- 6. Toric, extended wear, monovision or multi-focal contact lens correction.
- 7. Any previous or planned (during the course of the study) ocular surgery (e.g., PRK, LASIK, etc.).
- 8. Participation in any contact lens or lens care product clinical trial within 30 days prior to study enrollment.

- 9. Participation in clinical trials involving the Test lens within 3 months prior to study enrollment.
- 10. Employee or immediate family member of an employee of clinical site (e.g., Investigator, Coordinator, Technician).
- 11. Binocular vision abnormality or strabismus by self-report or prior medical history.
- 12. History of recurrent corneal erosions, herpetic keratitis, or pathological dry eye.

Exclusion Criteria after Baseline

- 13. Any active ocular allergies, infections or other ocular abnormalities (entropion, ectropion, extrusions, chalazia, recurrent styes, glaucoma) that the investigator determines may interfere with the outcomes of this study or otherwise contraindicate participation in the study.
- 14. Any Grade 2 or greater slit lamp findings (e.g., edema, corneal neovascularization, corneal staining, tarsal abnormalities, conjunctival injection) on the FDA Slit Lamp Classification Scale.
- 15. Any previous history or signs of a contact lens-related corneal inflammatory event (e.g., past peripheral ulcer or round peripheral scar) within the past 3 years of otherwise successful contact lens wear.

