## Slit Lamp Findings (Grade 3 or Higher)

Slit Lamp Findings will be assessed for each subject eye at all study visits (schedule and unscheduled). SLF is a binary response where Y=1 for at least one Grade 3 or 4 slit lamp finding. The percentage of eyes with Grade 3 or higher slit lamp findings will be analyzed and will include corneal infiltrates. Eyes with multiple events will be counted only once.

The FDA Biomicroscopy Scale measures the severity of the ocular clinical findings and goes from Grade 0 (none) to Grade 4 (severe). The procedure is explained in the section 12 Appendix D of the study protocol. The individual ocular finding results are considered as other endpoints.

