## 4. STATISTICAL HYPOTHESES FOR STUDY OBJECTIVES

#### 4.1. Primary Hypotheses

All the primary hypotheses must be met in order to satisfy the primary objective of this study.

- 1. Subjects wearing the JJVCI Investigational contact lenses on a daily wear basis will have patient reported comfort at the 2-Week Follow Up visit that is non-inferior to that of subjects wearing predicate device on a daily wear basis. A non-inferiority margin of -5 CLUE points will be used.
- 2. Subjects wearing the JJVC Investigational contact lenses on a daily wear basis will report distance monocular visual acuity (logMAR: bright room luminance / high contrast charts) at the 2-Week Follow Up visit that is non-inferior to that of subjects wearing predicate device on a daily wear basis. A non-inferiority margin of 0.05 LogMAR will be used.
- 3. Subjects wearing the JJVCI Investigational contact lenses on a daily wear basis will have patient reported outcome (Agree and Strongly Agree) on the Quality of Vision in Bright Light at the 2-Week Follow Up visit that is non-inferior to that of subjects wearing predicate device on a daily wear basis. A non-inferiority margin of 10% will be used.
- 4. Subjects wearing the JJVC Investigational contact lenses on a daily wear basis will have a percentage of any grade 3 or higher slit lamp findings at all visits (scheduled and unscheduled) that is non-inferior to that of subjects wearing predicate device on a daily wear basis. A non-inferiority margin of 5% will be used.
- 5. At least 90% of eyes wearing the JJVC Investigational contact lenses on a daily wear basis will have acceptable fits across the fitting and follow-up visits.

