#### Table 9: Descriptive Summary of Slit Lamp Findings Pooled Across all Historical Studies

SLF Grade 2	Test n (%)	Control n (%)
Corneal Edema	0 (0.0)	0 (0.0)
Conjunctival Injection	59 (6.86)	59 (21.85)
Tarsal Abnormalities	51 (5.93)	24 (8.89)
Corneal Neovascularization	3 (0.35)	0 (0.0)
Corneal Staining	3 (0.35)	0 (0.0)
Other Findings	0 (0.0)	0 (0.0)
Total Eyes (N)	860	270
	·	
Any SLF Grade 2 	116 (13.48)	83 (33.74)
Any SLF Grade 3+	0 (0.0)	0 (0.0)
Total Unique Eyes	860	270
Total Unique Subjects	430	135

%= nx100/N; SD=Standard Deviation

All SLF reported for this study are combined for the purposes of summarizing

 The percent (%) of Any Grade 2 is calculated using the Total Unique Eyes as the denominator

Table 10: Descriptive Summary of Individual Ite	em from – 2-Weel	- 2-Week Follow-up	
Questionnaire Item/ Response	Test	Control	
Vision Satisfaction in Bright Light [n(%)]			
Strongly Agree	72 (29.75)	51 (21.07)	
Agree	129 (53.31)	130 (53.72)	
Neither Agree Nor Disagree	24 (9.92)	21 (8.68)	
Disagree	17 (7.02)	33 (13.64)	
Strongly Disagree	0 (0.0)	7 (2.89)	

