#### Slit Lamp Findings

There were no Grade 3 or higher SLFs observed in any of the historical studies. Assuming no difference between study lenses and a correlation 0.70 between left and right eyes within the same subject (intra-subject correlation), a reference rate of no more than 5% was assumed (worse-case scenario) with a non-inferiority odds ratio margin of 2. A total of 2000 replicating trials were simulated, each replicated sample was analyzed using a generalized estimating equation (GEE) model with a binary distribution and the logit as the link function. Each model included lens type as the only fixed, eye was included as a random effect. The Odds ratio and corresponding 95% confidence interval was used estimate differences between the Test and Control lenses. The upper limit of each 95% confidence interval was compared to 2; if the upper limit was below 2 then NI=1; otherwise NI=0. Statistical power was calculated at the average NI. A sample size of 224 (112 per arm) was chosen to achieve a minimum statistical power of 80%.

Using a reference rate for the control that does not exceed 5% and no more than a 5% difference between the Test and Control lenses translates to an odds ratio margin of 2. A reference rate of 5% was used since this is the worst-case scenario.

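### If Grade 3+ slit lamp findings are few, the must-pass safety test appears to move to Grade 2+ at the same 5-point margin, with no trigger, margin rationale or power

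*SAP*

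**What the plan says.** SAP 10.1 (Slit Lamp Findings, Hypothesis Testing) tests the difference in proportions of eyes, Test minus Control. The upper limit of the two-sided 95% credible interval must lie below 0.05. The section then adds a fallback: if "the number of Grade 3 or higher SLFs is too small Grade 2 or higher SLFs will be analyzed and tested as described above". Protocol 14.5 has the same sentence. Just before it, both documents allow reduced versions of the model if the full one does not converge.

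Elsewhere the endpoint is Grade 3+ alone:

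- SAP 4.1, hypothesis 4, concerns the "percentage of any grade 3 or higher slit lamp findings at all visits". SAP 4.1 also requires all five primary hypotheses to be met.
- SAP 3.1 defines the response: "SLF is a binary response where Y=1 for at least one Grade 3 or 4 slit lamp finding". Corneal infiltrates count in it.
- SAP 7.4 ties the margin to a "reference rate for the control that does not exceed 5" percent, and the only slit lamp row in the power table is Grade 3 or higher.
- SAP 7.4 also records the history: "There were no Grade 3 or higher SLFs observed in any of the historical studies".

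**The concern.** The rule has no number in it. It does not say what count is too small, whether the count is taken over both arms or by arm, or who judges it and when relative to unmasking. It also does not say whether Grade 2+ replaces Grade 3+ for hypothesis 4 or is added to it.

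Few or no Grade 3+ findings is the best result this endpoint can show. Yet that result would send the must-pass test to a different and commoner endpoint, with a margin that was not argued for it and a sample size that was not checked for it. If the two endpoints can give opposite answers, an undefined trigger can decide whether the study meets its objective.

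**Working it through.** **Inputs.** SAP 7.4 gives 112 completers per arm and the planning case "Assuming no difference between study lenses and a correlation 0.70 between left and right eyes". SAP 10.1 gives the 0.05 margin and the 95% interval. SAP Table 2 gives 116 randomized per arm. SAP Table 9 gives the historical counts. I assume that the 0.70 correlation carries over to Grade 2+, and I vary it.

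**The plan's own figure.** SAP 7.4 states 80% power for Grade 3+ at 5% in both arms, with an odds ratio margin of 2.

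- Effective eyes per arm: 2 × 112 / (1 + 0.70) = 131.8.
- SE of the log odds ratio: √[2 / (131.8 × 0.05 × 0.95)] = 0.565.
- Power: Φ(ln 2 / 0.565 − 1.96) = 23%.

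On the risk-difference scale that SAP 10.1 actually tests, the same inputs give 46%, or about 48% by simulation. So 80% does not reproduce. That is a separate matter, and nothing below uses it.

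**How likely is the switch?** Table 9 shows 0 of 860 Test eyes and 0 of 270 Control eyes with Grade 3+. Enrolment in the historical studies sums to 135 + 133 + 92 + 54 + 56 = 470 subjects. Given 0 of 470, the predictive chance of no affected subject among 232 is 82% with a Beta(0.5,0.5) prior and 67% with Beta(1,1). The switch is likely but not certain, because infiltrates count in the endpoint and have no row in Table 9.

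**Does the margin carry over?** Five points above a 5% control rate is an odds ratio of (0.10/0.90)/(0.05/0.95) = 2.11, close to the planning margin of 2. From 13.5% it is 1.46, and from 30.7% it is 1.25. The stated rationale therefore does not extend to higher rates.

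**Chance that the Grade 2+ test passes when the lenses are equal.** SE = √[2p(1 − p)/131.8], and the pass rate is Φ(0.05/SE − 1.96). At p = 13.48%, SE = 0.0421, so Φ(1.188 − 1.96) = 22%. The simulations use paired eyes and a robust variance:

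| Grade 2+ eye rate, both arms | Formula, 0.7 | Simulated, 0.7 | Simulated, 0.3 | Simulated, 0 |
|---|---|---|---|---|
| 2% | 83% | 82% | 89% | 95% |
| 5% | 46% | 48% | 58% | 68% |
| 6.9% | 36% | 38% | 46% | 56% |
| 13.5% | 22% | 23% | 28% | 34% |
| 30.7% | 14% | 14% | 17% | 21% |

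The range 2% to 30.7% is an assumption. Its upper values come from Table 9: Test 116/860 = 13.5%, and Control 83/270 = 30.7% (printed as 33.74%). Both counts equal the sums of the separate findings (59 + 51 + 3 + 3 = 116; 59 + 24 = 83), so some eyes may be counted twice. The 6.9% is conjunctival injection alone in Test eyes.

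**If the historical rates held.** With Test at 13.5% and Control at 30.7%, the simulated pass rate is about 99%.

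**Grade 3+ with no events.** With 0 v 0 of 116 subjects and a Beta(0.5,0.5) prior, the 97.5% limit of the difference is 1.35 points under the correlated-binary likelihood that SAP 10.1 uses for lens fit. It is 1.9 points at subject level. Both are below 5.

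**The case against.** The best case for the plan has four parts.

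- The fallback is prespecified, in the same words in both documents, so it is not a post hoc change. That is true. But a rule without a threshold still leaves the choice of endpoint open once counts are known.
- The sentence says that Grade 2+ will be tested, not that it decides hypothesis 4. That is also true. Substitution is the ordinary reading, and the documents should settle it.
- With 0 v 0, Grade 3+ passes on sample size and prior alone, so a commoner finding is a sensible safety check. This supports reporting Grade 2+. It does not supply a margin or a sample size for a pass/fail test.
- The only Grade 2 data favour the Test lens, and equality and the 0.70 correlation were set for sizing Grade 3+. This stands as a limit on the conclusion.

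A reader might infer that an equal lens will probably fail. The documents do not support that. "Any Grade 2 or greater slit lamp findings" at baseline is an exclusion in protocol 3.3, so on-study rates may differ from history, and the Table 9 footnote says "All SLF reported for this study are combined for the purposes of summarizing". The historical arms are pooled and not fully randomized, so neither the 99% nor the low figures can be taken as the forecast.

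A reader might also infer from the SAP 14.1 listing, whose contrast sets the random effects to zero, that the switched test would let a worse lens pass. I do not rely on this. The listing fits age and sex, and its contrast leaves out the age term, so it is evaluated at age 0 in a trial of ages 18 to 49. Any figure would have to allow for that. The scale of the contrast also affects Grade 3+ and is a separate issue.

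**Conclusion.** The point holds as a gap in a must-pass test. The trigger, the role of Grade 2+, its margin and its power are all unstated, and the rule is likely to be invoked. The two endpoints can disagree: Grade 3+ with no events clears the margin easily, while Grade 2+ in equal lenses passes anywhere from about 82% down to 14% of the time as its rate goes from 2% to 30.7%. These figures rest on equal true rates, correlation 0.7, 112 per arm, the eye-proportion scale and no site or covariate terms. Lower correlation raises them but does not remove the problem at rates of 5% or more. Failure of an equal lens is therefore possible, not established. The plan should be changed before database lock.

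**What to change.** In SAP 10.1 and protocol 14.5, delete the switch. Keep Grade 3+ as the only tested endpoint for hypothesis 4. Report Grade 2+ by arm as supportive, with an interval and no pass/fail role.

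Name now the reduced model for sparse Grade 3+ data, with a stated trigger on the pooled, masked count. One option is the correlated-binary likelihood that SAP 10.1 gives for lens fit, with the Beta(0.5,0.5) prior of SAP 14.1. It would be run by arm, the posteriors differenced, and the 97.5% limit compared with 0.05.

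If the sponsor prefers to keep a switch, it should state a numeric trigger on the pooled masked count, say whether Grade 2+ replaces Grade 3+, and give Grade 2+ its own margin, power and contrast scale.

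The cost is wording in two documents and a short code addition: the lens-fit listing runs by arm but forms no difference, and it uses a variable z that it does not define. There are three downsides. There is no formal Grade 2+ test. The reduced analysis drops the site, baseline and covariate terms. A split of 2 v 0 affected subjects is borderline: the limit is 4.5 points if both eyes are affected (4.9 with Beta(1,1)) but 5.1 at subject level, so the likelihood and prior must be fixed in advance.
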